- 3) VAP caused by a MDR pathogen: Early VAP is rarely caused by MDR pathogens; in a recent analysis of our surgical ICU, 94% of cases of early VAP were caused by highly sensitive pathogens (Methicillin-sensitive staphylococcus aureus 39%, Haemophilus influenza 35%, Streptococcus pneumoniae 16%, Esterichia coli 9%) [14]. Patients with early VAP caused by the following MDR pathogens will be excluded: Methicillin-resistant Staphylococcus aureus (MRSA), Vancomycin-intermediate Staphylococcus aureus (VISA), pseudomonas aeruginosa, Vancomycin-resistant enterococcus (VRE), Acinetobacter baumannii, Stenotrophomonas maltophilia, carbapenem-

resistant enterobacteriaceae (CRE), and extended-spectrum beta lactamase producing gram negative bacilli.

- 4) Causative pathogen not sensitive to choice of initial empiric antibiotic.
- 5) Antibiotic therapy for ≥ 5 of the last 10 days preceding the BAL.
- 6) Septic shock, defined as evidence of tissue hypoperfusion after adequate volume expansion, due to infection, and requiring ≥ 1 vasopressor [17].
- 7) Current or recent (within 30 days) use of immunosuppressive medications.
- 8) Length of stay ≥ 72 hours in a transferring facility.
- 9) Pregnancy or lactation.
- 10) Legal arrest or incarceration.
- 11) Moribund state in which death is imminent.

Outcomes:

The two main outcomes will be effectiveness of treatment and antibiotic exposure.

Effectiveness of treatment will be assessed in three ways: 1) Clinical response, 2) MR, and 3) biomarker response.

Clinical Response: Current guidelines state that appropriately treated patients with VAP should have a favorable clinical response by day 3, and a substantial improvement by day 6 [9]. Clinical variables used to assess for treatment response are organized into the Clinical Pulmonary Infection Score (CPIS). The original CPIS, as described by Pugin et al. [18], included five clinical variables [temperature, white blood

cell count (WBC), tracheal secretions, ratio of P_aO_2 to F_iO_2 (P:F), and chest radiograph findings) and one microbiologic variable (culture of tracheal aspirate and its relationship to the gram stain). Several authors have since modified the score to exclude the microbiologic variable in order to both screen for VAP and monitor efficacy of treatment [11, 19]. This modified score, herein referred to as CPIS_{clinical}, omits the microbiologic variable and ranges from 0-10.

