Currently, procalcitonin concentration is measured in all surgical ICU patients for whom a BAL is sent on the day of the BAL as part of a separate non-interventional study. For the purposes of the current trial, procalcitonin concentration will also be measured during treatment in order to assess response, as well as following treatment in order to assess for recurrence. Because study entry will occur at the time that VAP is confirmed microbiologically (approximately 72 hours following the BAL and initiation of empiric antibiotics), these measurements will begin after three days of antibiotic therapy. Procalcitonin concentration will then be measured daily for the remainder of treatment, as well as daily for 72 hours following treatment. Thus, the 4 day group will have procalcitonin concentration measured at baseline, treatment days 3 and 4, and post treatment days 1-3. The 8 day group will have procalcitonin measured at baseline, treatment days 3-8, and post-treatment days 1-3. The treatment team will have access to the results of these measurements. For the purposes of the trial, biomarker resolution will be defined as a procalcitonin concentration $< 0.5 \mu\text{g/L}$ or a decrease of $\geq 80\%$ relative to the day of the BAL [26].

Additional Outcomes: Days of antibiotics, antibiotic days (defined as the product of days of antibiotics and number of antibiotics per day), recurrence, ventilator days, empyema, need for tracheostomy, non-pulmonary infections, ICU length of stay (LOS), hospital LOS, and mortality. Recurrence is defined using the same clinical and microbiologic criteria as the initial episode of VAP, and occurring 2-14 days

following completion of initial therapy. Relapse is defined as recurrent VAP caused by the initial pathogen; super-infection is defined as recurrent VAP caused by ≥ 1 new pathogen. VAP occurring > 14 days following completion of initial therapy will be considered a second episode of pneumonia as opposed to a recurrence. The incidence of recurrent VAP due to a MDR pathogen, as well as any other infection caused by a MDR pathogen, will also be abstracted.

Baseline Variables: Age (years), gender, admission diagnosis, associated diagnoses, admission APACHE II score, comorbidity index [27], prior and current antibiotic exposure, base deficit, serum lactate concentration, time from ICU admission to BAL, presence of organisms on gram stain, and presence of polymorphonuclear lymphocytes on gram stain.

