Study Flow & Stop Criteria: The trial will be reported in accordance with the recommendations of the CONSORT Statement [28]. IRB approval will be obtained. All subjects or their legally authorized representative will provide written consent for study participation. The trial is registered with the US National Institutes of Health (ClinicalTrials.gov Identifier NCT01994980).

Screening will occur daily by study personnel. Eligible patients will be approached as soon as possible after inclusion criteria are met (i.e., 1-3 days prior to randomization). Randomization will occur using a computer-generated block pattern on the morning following the fourth day of appropriate antibiotic therapy.

Empiric antibiotic therapy will be instituted as soon as possible following BAL acquisition. The default antibiotic will be ceftriaxone 2 gram IV q24 hours. Patients with potential allergies to cephalosporins will receive levofloxacin 750 mg IV q24hours. Pre-existing treatment for a non-

pulmonary infection with at least one antibiotic that has appropriate activity against the VAP pathogen may be substituted for the default antibiotic. Once sensitivity data become available (approximately 72 hours after BAL acquisition), therapy may be de-escalated to a more narrow-spectrum agent (e.g., cefazolin) as indicated.

The default duration of antibiotic therapy will be determined by study group assignment; the treatment team will be asked to adhere to study group assignment whenever possible. However, the treatment team may choose to extend the duration of antibiotic therapy based on clinical circumstances, such as deterioration in hemodynamic or respiratory status that is believed to be related to incompletely treated VAP, or continued treatment of a non-pulmonary infection. The treatment team may also decide to extend the duration of antibiotic therapy based on the results of serial procalcitonin measurements. Finally, the treatment team may decide to extend the duration of antibiotic therapy based on the results of the BAL obtained the day after completion of therapy. These clinical decisions will take precedence over study group assignment.

Patients will be followed for 28 days or until hospital discharge, whichever occurs first. Please see attached data collection tool for detailed information.

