Kolmogorov-Smirnov test. Differences in the means of continuous variables that are distributed normally will be assessed using the Student's t-test. Differences in the medians of continuous variables that are not distributed normally will be assessed using the Wilcoxon Rank Test. Proportions of categorical variables will be compared using the chi-squared test. When expected cell counts are < 5, Fischer's exact test will be used. Univariate analysis of categorical outcomes will be expressed as the relative risk with 95% confidence intervals. A logistic regression model will be fit to address possible confounding by differences in baseline parameters between groups. Baseline variables associated with randomization status at the $p<0.25$ level by univariate analysis will be added to the model using a forward selection method. The overall contribution of the fitted model to predicting variability in the outcome of interest will be assessed using the likelihood ratio chi-squared test. The independent contribution of individual variables will be assessed using the Wald chi-squared test. Model fit was will be assessed using the Hosmer-Lemeshow goodness-of-fit chi-squared statistic, with $p>0.05$ indicating acceptable model calibration. The alpha error level is defined at 0.05, with statistical significance set at $p<0.05$.

Adverse Event Monitoring and Reporting: Adverse event monitoring will occur daily. The safety of the study will be monitored by an independent, external Data Safety Monitoring Board, consisting of a medical intensivist, and an infectious disease physician. The committee will meet biannually and submit written reports to the IRB.

References:

1. Edwards, J.R., K.D. Peterson, Y. Mu, S. Banerjee, K. Allen-Bridson, G. Morrell, et al., National Healthcare Safety Network (NHSN) report: data summary for 2006 through 2008, issued December 2009. *Am J Infect Control* 2009;37:783-805
2. Neu, H.C., The crisis in antibiotic resistance. *Science* 1992;257:1064-73
3. Mahgoub, S., J. Ahmed, and A.E. Glatt, Completely resistant *Acinetobacter baumannii* strains. *Infect Control Hosp Epidemiol* 2002;23:477-9
4. Kollef, M.H. and V.J. Fraser, Antibiotic resistance in the intensive care unit. *Ann Intern Med* 2001;134:298-314
5. Bradley, J.S., R. Guidos, S. Baragona, J.G. Bartlett, E. Rubinstein, G.G. Zhanel, et al., Anti-infective research and development--problems, challenges, and solutions. *Lancet Infect Dis* 2007;7:68-78

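### Ventilator days and length of stay are tested as raw counts that death ends, so an arm with more early deaths can look quicker to recover

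*Combined protocol and SAP*

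**What the plan says.** The Outcomes section states: "The two main outcomes will be effectiveness of treatment and antibiotic exposure". The Additional Outcomes paragraph then names the measures: "Days of antibiotics, antibiotic days (defined as the product of days of antibiotics and number of antibiotics per day), recurrence, ventilator days", and later in the same list "ICU length of stay (LOS), hospital LOS, and mortality". Each duration is a plain count, and mortality stands beside them as its own item.

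Under Study Flow & Stop Criteria, "Patients will be followed for 28 days or until hospital discharge, whichever occurs first". The sentence does not say what day 28 is counted from. Randomization takes place "on the morning following the fourth day of appropriate antibiotic therapy".

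The Data Analysis section covers all continuous outcomes with two rules: "Differences in the means of continuous variables that are distributed normally will be assessed using the" Student's t-test, and "Differences in the medians of continuous variables that are not distributed normally will be assessed using the Wilcoxon Rank Test". The summary statistic is the median with the range. The text supplied contains no ventilator-free days, no rank for death, no censoring rule, no competing-risk analysis and no summary by survival status. The logistic model addresses baseline imbalance, not death.

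**The concern.** A patient who dies on the ventilator three days after randomization contributes three ventilator days and a three-day stay from that point. A patient who is extubated on day 3 and recovers contributes the same ventilator count. The t-test and the Wilcoxon test cannot tell them apart, and both read a small value as a good result. If one arm has more early deaths, its durations shorten for that reason alone.

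The trial asks whether a shorter course is as effective as a longer one, so equal mortality cannot be taken for granted. A recovery measure that moves the wrong way when deaths rise could be read as support for the arm that did worse.

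Antibiotic exposure needs separate treatment because it is a main outcome and because randomization comes after four days of therapy. There the questions are which antibiotics are counted and over what period.

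**Working it through.** The plan gives no figure on this point, so there is none to reproduce. It gives no mortality rate and no distribution of durations either; those inputs are assumptions, shown as ranges. The group sizes of 51 and 52 split the planned total of 103 from the Power analysis.

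**1. Hand arithmetic on ventilator days.** Assume survivors are ventilated for 14 days, deaths occur at day 8, and mortality is 10% in one arm and 20% in the other.

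- Raw days: 0.1×8 + 0.9×14 = 13.4; 0.2×8 + 0.8×14 = 12.8. The arm with more deaths looks 0.6 days better.
- Days alive and ventilator-free to day 28 (death = 0, survivors 28 − 14 = 14): 0.9×14 = 12.6; 0.8×14 = 11.2. The same arm is 1.4 days worse.
- With 15% in place of 20%: raw 13.1 (−0.3 days), ventilator-free 11.9 (−0.7 days).

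**2. Simulation with spread-out durations.** Time to extubation is identical in both arms (log-normal, capped at 28 days) and unrelated to time of death. Deaths are uniform over days 0–7, with 10% mortality in the 8-day arm. Mean differences, 4-day minus 8-day:

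| 4-day mortality | Raw, median 8 d | Ventilator-free, median 8 d | Raw, median 14 d | Ventilator-free, median 14 d |
|---|---|---|---|---|
| 15% | −0.3 | −0.9 | −0.6 | −0.6 |
| 20% | −0.7 | −1.8 | −1.2 | −1.3 |
| 30% | −1.3 | −3.6 | −2.4 | −2.5 |

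A negative raw difference reads as faster recovery in the 4-day arm; a negative ventilator-free difference reads as worse. Later deaths weaken the effect: spread over days 0–14, 30% vs 10% at median 8 gives a raw difference of −0.9 in place of −1.3.

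**3. Error rate of the planned test.** Median 8 days, 51 vs 52 patients, two-sided 0.05. The share of trials in which the Wilcoxon test calls the 4-day arm significantly shorter is about 2% at 10% vs 10% mortality, 9–10% at 20% vs 10%, and 24–26% at 30% vs 10% (ranges over repeated runs). With days alive and ventilator-free, the share wrongly favouring the 4-day arm is about 2%, 0.2% and 0%.

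**4. Antibiotic days.** Every randomized patient already has 4 days. Count 24 further days (28 − 4), and let q be the assumed fraction of later days alive on antibiotics. Deaths are uniform over days 0–7 after randomization, so the mean time to death is 3.5 days.

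- 4-day arm: 4 + q×[(1 − m)×24 + m×3.5]. The bracket is 21.95 at m = 10% and 19.90 at m = 20%.
- 8-day arm at 10% mortality: patients who die receive on average 20/7 = 2.857 of the remaining 4 days, and have 4.5/7 = 0.643 later days. Exposure is 4 + 0.9×4 + 0.1×2.857 + q×(0.9×20 + 0.1×0.643) = 7.886 + 18.064q.
- Difference, 4-day minus 8-day, as 4-day mortality goes from 10% to 20%: q = 0, −3.89 and −3.89; q = 0.2, −3.11 and −3.52; q = 0.4, −2.33 and −3.15.
- Deaths in the 8-day arm at 20% and in the 4-day arm at 10%, with q = 0: 4 − (4 + 0.8×4 + 0.2×2.857) = −3.77. The saving narrows from 3.89 to 3.77.

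**5. Why the counting rule matters.** The Power analysis projects recurrence of 35% after 4 days against 25%. If each re-treatment lasted 8–14 days (an assumption, borrowing the guideline range in the Background), the extra 0.10 recurrences per patient would add 0.8–1.4 antibiotic days per patient, or 20–35% of the nominal 4-day saving. Counting or omitting them changes the result visibly.

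**The case against.** The strongest reply concerns antibiotic exposure. A reader might infer that this main outcome rewards death in the 4-day arm. The documents do not support that. Because randomization follows the fourth day, death cannot shorten the assigned course in the 4-day arm. In the 8-day arm it can remove at most four days, which works against the 4-day arm. Bias toward 4 days needs later antibiotics to be counted, and even then it enlarges an existing difference without creating one. A patient who died also did receive fewer antibiotics, so for selection pressure the raw count is a fair measure. This stands.

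A reader might also infer that there is no observation period, or that re-treatment is left out. Follow-up is capped at 28 days or discharge, and nothing in the outcome list excludes treatment of recurrences. What remains is narrower: no start point is given, discharge ends the count at different times, and inclusion of re-treatment is not stated. The attached data collection tool may settle some of this and could not be seen.

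The two-point example compares means, whereas the plan reports medians. With those inputs the median is 14 in both arms, and about 5 of 51 vs 10 of 52 short values give a Wilcoxon p of about 0.18. That is fair, and it is why the simulation uses the planned test on realistic spreads.

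Finally, moribund and septic-shock patients are excluded, mortality is reported, and an external board monitors safety. These lower the number of deaths or make an imbalance visible. They do not correct the duration comparisons.

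**Conclusion.** The concern holds for ventilator days, ICU stay and hospital stay. As planned, these comparisons favour whichever arm has more early deaths. With identical recovery, the raw difference in ventilator days is about 0.3 to 2.4 days for an excess mortality of 5 to 20 percentage points, and the false-positive rate in favour of that arm rises from about 2% to about 24–26% at the upper end. All of this rests on assumed mortality, early deaths, and time of death unrelated to time to extubation. With equal mortality there is no bias between arms.

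For antibiotic exposure the effect of death is weaker and its direction depends on what is counted. The point there is a counting rule that should be written down before data are seen. It is not a finding that the main outcome credits death as benefit.

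**What to change.** - **Ventilator days:** make days alive and ventilator-free to day 28, with death scored 0, the tested version. Show raw days as description, by survival status.
- **ICU and hospital stay:** test days alive and out of the ICU or hospital to day 28, or analyse time to discharge alive with death as a competing event. Show raw stay by survival status.
- **Antibiotic exposure:** count all antibiotics, including re-treatment of recurrence, from the BAL to day 28, discharge or death. Keep raw antibiotic days as the main exposure measure and add antibiotic days per day alive as a supporting analysis. Antibiotic-free days with death scored 0 should not replace the raw count, because that would turn an exposure measure into a partial mortality measure.
- **Day 28:** state the day from which it is counted.

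These are mostly derived variables, and nothing in treatment changes. There are two costs. Free-days mix death with duration, so mortality and raw days must be shown beside them. Follow-up ends at discharge, so patients discharged alive off the ventilator must be assumed to stay off it to day 28, with ventilator and antibiotic status at discharge recorded. Days out of hospital need a similar assumption about survival and readmission; the competing-event analysis of discharge avoids it.

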One subset of patients for whom a decreased duration of antimicrobial therapy may be particularly effective is those who develop VAP \leq 7 days after intubation (early VAP). Early VAP comprises the majority of cases of pneumonia diagnosed in the ICU[14] . Furthermore, as compared to patients who develop late VAP, patients who develop early VAP are more likely to be infected with community-acquired pathogens sensitive to narrow spectrum antibiotics [14]. Finally, nearly all cases of

early VAP caused by sensitive pathogens demonstrate MR after relatively short (3-5 days) courses of therapy [10].

The hypothesis of this randomized clinical trial (RCT) is that 4 days of antibiotic therapy, as compared to 8 days, is equally effective and results in decreased antibiotic exposure among surgical ICU patients with early VAP.

Methods:

Study Design: Randomized, double-blind (until treatment day 5) clinical trial.

Intervention: Default 4 vs. 8 days of antibiotic therapy.

Screening Pool: Trauma-Surgical ICUs.

Inclusion Criteria:

- 1) Surgical patient
- 2) Early VAP, defined as:
 - a. Duration of Intubation: 2-7 days [9] (via endotracheal or tracheostomy tube).

- b. Clinical suspicion of pneumonia: New or progressing infiltrate on chest radiograph (CXR) along with ≥ 1 of the following: Temperature $\geq 38.5^{\circ}\text{C}$ or $< 36.5^{\circ}\text{C}$; blood leukocytes $>11,000 \text{ mm}^3$ or $<4,000 \text{ mm}^3$; purulent tracheal secretions; or $\text{PaO}_2:\text{FiO}_2 < 200$ [15].
- c. Quantitative microbiologic confirmation: Bronchoalveolar lavage (BAL) culture showing $\geq 10^5 \text{ cfu/mL}$ of at least one pathogen [16]. The quantitative microbiology threshold will be lowered to $\geq 10^4 \text{ cfu/mL}$ if the patient was being treated with antibiotics to which the pathogen is sensitive at the time of the BAL.

3) Hospital LOS ≤ 10 days at the time that the BAL was obtained.

Exclusion Criteria:

- 1) Age < 18 years.
- 2) Prior episode of VAP for the index admission (the patient may have had prior BALs sent for culture, but these cannot have met the above mentioned diagnostic criteria for VAP).

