The CPIS_{clinical} will be calculated at baseline and daily thereafter during the study period. In the case that certain individual variables are not available for abstraction, they will be left blank rather than obtained solely for the purpose of the study. The worst values (those associated with the highest number of points) for each variable over the 24 hours prior to the BAL will be used. Tracheal secretions will be scored based on daily progress notes from the respiratory therapist. Chest radiograph findings will be scored based on attending final radiologist reads.

It is important to note that CPIS_{clinical} possesses limited accuracy for monitoring VAP resolution in surgical ICU patients [20, 21]. Furthermore, a multicenter RCT reported decreased organ failure, mortality, and antibiotic use for patients with suspected VAP managed using a microbiologic endpoint as compared to a clinical one [22]. For these reasons, efficacy of treatment will also be assessed both microbiologically and using a biomarker of infection (*see below*).

Microbiologic Response: The definition of microbiologic response for VAP reported most commonly ranges from $<10^2$ cfu/mL [23] to $<10^3$ cfu/mL [10] from a repeat BAL culture obtained the day after the end of therapy. For the purposes of this trial, microbiologic response will be defined as growth of the original pathogen of $<10^3$ cfu/mL from a BAL culture obtained the day after the end of treatment. Repeat BALs will thus be obtained on day 5 for the 4-days of antibiotics group and day 9 for the 8 days of antibiotics group. If the patient is no longer intubated at this time, a repeat BAL will not be obtained and MR will be inferred. The treatment team will have access to the results of the repeat BAL.

Biomarker Response: Circulating levels of calcitonin precursors, including procalcitonin, are elevated in bacterial infections [24, 25]. Normalization of procalcitonin concentration in patients receiving therapy for VAP has been shown to both correlate with clinical response and guide discontinuation of antibiotics [26]. The relationship between clinical response, MR, and procalcitonin concentration has not been evaluated prospectively in critically ill patients being treated for VAP and will be the focus of a sub-analysis.

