Sample acquisition and processing: The default method for BAL specimen acquisition will be via the blind or “mini” BAL technique [18], using an 85 mm by 4 mm bronchial diagnostic catheter (Combicath, ® Prodimed, Neuilly-en-Thelle, France). The catheter is passed through the artificial airway until resistance is met. It is then withdrawn approximately 1 cm and the inner lavage catheter is deployed. Lavage is then performed with 20 – 40 mL of sterile saline.

The BAL will be obtained bronchoscopically if bronchoscopy is being performed for another indication (e.g., pulmonary toilet, percutaneous dilational tracheostomy). Lavage is performed using 20-40 mL of normal saline lavage into the lobar bronchus that appears most abnormal on CXR.

Using a 0.001 calibrated loop, vortexed BAL specimens will be plated onto sheep blood, MacConkey, and Chocolate agar at 35°C - 37°C in CO₂. Plates will be examined after 24, 48, and 72 hours prior to issuing a final negative report. 100 or more colonies per plate is considered significant and represents $\geq 10^5$ cfu/mL.

Statistical Analyses:

Power analysis: Power analysis was performed using SAS Version 9.1 (SAS, Inc., Carey, NC, *proc power*). The Analysis was based on a non-inferiority study design, defined as a difference in outcomes between the 4 day and 8 day groups of < 10%. Furthermore, as the intention was to show non-inferiority, tests were one-sided using an alpha error level of 0.10. The beta error level was set at 0.20 for 80% power. Analysis for the outcome of VAP recurrence returned the largest sample size. From 2010-2012, during which time VAP was treated with ≥ 8 days of therapy, the incidence of recurrent VAP in the DHMC surgical ICU was approximately 25%. Projecting a recurrence rate after 4 days of treatment of 35% returns a total sample size of 103..

Interim Analysis: An interim analysis will be conducted for all outcomes after 50% accrual (n_{total}=50).

Data Analysis: Data analyses will be performed using SAS Version 9.1 (SAS, Inc., Carey, NC). Data will be analyzed using an intention-to-treat strategy (i.e., patients randomized to receive 4 days of antibiotic therapy will be analyzed with this group even if they receive longer courses). Data will be expressed as median (range) or number (%). Normality of continuous variables will be assessed using the

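### Pneumonia re-treated after extubation without a quantitative BAL is not counted as recurrence, so the outcome that sized the trial may be under-counted, with bias of uncertain direction

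*Combined protocol and SAP*

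**What the plan says.** Outcomes, Additional Outcomes, defines the event: "Recurrence is defined using the same clinical and microbiologic criteria as the initial episode of VAP", falling 2 to 14 days after initial therapy ends. Inclusion criterion 2c supplies the microbiologic part: "Quantitative microbiologic confirmation: Bronchoalveolar lavage (BAL) culture showing" at least 10^5 cfu/mL of a pathogen, or 10^4 if the patient was on active antibiotics.

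Sample acquisition and processing describes two routes to a BAL. For the default mini-BAL, "The catheter is passed through the artificial airway until resistance is met". For the other, "The BAL will be obtained bronchoscopically if bronchoscopy is being performed for another indication".

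Outcomes, Microbiologic Response, says how extubated patients are handled at the end-of-treatment culture: "If the patient is no longer intubated at this time, a repeat BAL will not be obtained and MR will be inferred".

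After the antibiotic-exposure measures, the additional outcomes are "recurrence, ventilator days, empyema, need for tracheostomy, non-pulmonary infections, ICU length of stay (LOS), hospital LOS, and mortality". Recurrent VAP due to an MDR pathogen is also recorded, "as well as any other infection caused by a MDR pathogen, will also be abstracted".

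The Power analysis names VAP recurrence as the outcome that gave the largest sample size.

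**The concern.** A shorter course could plausibly cause late relapse, and recurrence is the outcome meant to detect it. A patient who improves, is extubated, and then develops a new infiltrate that is treated with a further antibiotic course will usually have no quantitative BAL. On the plan's definitions that patient has no recurrence and, if already extubated when the repeat BAL was due, also has an inferred microbiologic response. The same patient can thus count as a success on two effectiveness measures while being treated again for pneumonia.

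At stake is the comparison on which the trial was sized. Events missing from a non-inferiority comparison are not neutral. Depending on how the loss falls between the arms, they can bring the recorded difference inside the margin or push it outside.

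**Working it through.** **1. The plan's own figure.** The Power analysis gives a total of 103 (25% vs 35%, 10-point margin, one-sided alpha 0.10, 80% power). It does not reproduce as a two-arm total. Non-inferiority with both arms at 25% needs 170 per arm, 340 in all. A one-sample formula gives 0.35 × 0.65 × (1.2816 + 0.8416)² / 0.10² = 102.55, i.e. 103. That is a separate matter. Here 103 serves only as the planned size, taken as 51.5 per arm because the allocation ratio is not stated (1:1 assumed).

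**2. Where a post-extubation pneumonia can land.** Take a pneumonia inside the recurrence window, re-treated, with no re-intubation and no bronchoscopy.

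| Listed outcome | Does it record the event? |
|---|---|
| Recurrence (relapse, super-infection) | No: no quantitative BAL |
| Microbiologic response | Inferred as a success if extubated when the repeat BAL was due |
| Non-pulmonary infections | No, by its label |
| Empyema | Only if it develops |
| MDR infection | Only if the organism is MDR |
| Days of antibiotics, antibiotic days | Yes, but as exposure, not as failure |
| CPIS_clinical, length of stay, mortality | Indirectly; missing CPIS items are left blank |
| Procalcitonin | Only within 72 hours after treatment |

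The MDR item is unlikely to catch a relapse with the initial pathogen. Exclusion criterion 3 removes index episodes caused by listed MDR organisms and reports that 94% of the site's early VAP came from highly sensitive pathogens.

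**3. Timing by arm.** With default durations, the window of 2 to 14 days after therapy is treatment days 6 to 18 in the 4-day arm (4 + 2 to 4 + 14) and 10 to 22 in the 8-day arm (8 + 2 to 8 + 14). The 8-day window opens and closes four days later, when more patients may be extubated, so equal loss cannot be taken for granted.

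**4. Direction.** Let f4 and f8 be the shares of recurrent pneumonias missed in each arm, with underlying total rates of 35% and 25% (an assumption; see step 6).

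Recorded difference = 0.35(1 − f4) − 0.25(1 − f8) = 0.10 − 0.35·f4 + 0.25·f8.

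It falls below 10 points when 0.35·f4 > 0.25·f8, that is, when f8 < 1.4·f4. With f4 = 20%, the turning point is f8 = 28%.

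**5. Illustration only.** The documents give no value for f4 or f8. P is the chance of declaring non-inferiority at the 10-point margin by normal approximation: P = Φ((0.10 − d)/SE − 1.2816), where SE² = [p4(1 − p4) + p8(1 − p8)]/51.5, p4 and p8 are the recorded rates, and d = p4 − p8.

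| Missed, 4-day | Missed, 8-day | Recorded, 4-day vs 8-day | Difference (points) | P |
|---|---|---|---|---|
| 0% | 0% | 35% vs 25% | 10.0 | 0.10 |
| 20% | 20% | 28% vs 20% | 8.0 | 0.15 |
| 30% | 30% | 24.5% vs 17.5% | 7.0 | 0.18 |
| 30% | 20% | 24.5% vs 20% | 4.5 | 0.27 |
| 40% | 20% | 21% vs 20% | 1.0 | 0.44 |
| 20% | 30% | 28% vs 17.5% | 10.5 | 0.09 |
| 20% | 40% | 28% vs 15% | 13.0 | 0.05 |

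**6. The base rate.** The 25% in the Power analysis is the unit's incidence of recurrent VAP, not of all recurrent pneumonia. It may already leave out post-extubation cases. If so, with 20% missed in both arms, recorded rates of 25% and 35% would correspond to underlying totals of 25/0.8 = 31.25% and 35/0.8 = 43.75%. The table therefore shows how the mechanism behaves; it does not estimate this trial's bias.

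**The case against.** A reader might infer that these events vanish from every outcome. They do not. Re-treatment raises days of antibiotics, and antibiotic exposure is one of the two main outcomes. MDR cases and empyema are recorded. A patient who is re-intubated, or has bronchoscopy for another reason, can still meet the definition. The recurrence sentence carries over the clinical and microbiologic criteria without naming the intubation-duration criterion. All of this stands, but none of these routes identifies a non-MDR pneumonia treated after extubation as a recurrence.

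A reader might also infer that the arms must look more alike, to the benefit of the 4-day arm. That follows only if the 8-day share missed is below 1.4 times the 4-day share, under the assumed rates. The later 8-day window makes greater loss there possible, and the documents contain no extubation data to settle it.

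Third, requiring a BAL is a reasoned choice. The Clinical Response section says that the clinical score has limited accuracy in surgical ICU patients. A chart-based outcome is less specific, and its false positives can also dilute the difference. If an assumed 10% of patients without recurrence were wrongly counted in each arm, 25% would become 25 + 0.10 × 75 = 32.5% and 35% would become 35 + 0.10 × 65 = 41.5%, a gap of 9.0 points. The design is blinded only until treatment day 5, so a team that may know the arm decides whether to re-treat. This limits the added outcome to a supportive role; it does not remove the gap.

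Finally, the attached data collection tool mentioned under Study Flow & Stop Criteria was not available. It may record other pneumonias. Even so, the outcome and analysis sections neither define nor analyse them.

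**Conclusion.** The gap is real and narrow. As written, a non-MDR pneumonia that returns after extubation and is re-treated without a quantitative BAL is not a recurrence, and it is not any listed infection outcome short of empyema. Recurrence may therefore be under-counted.

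Neither size nor direction can be fixed from the documents. Equal proportional loss, or greater loss in the 4-day arm, shrinks the difference and favours non-inferiority. Loss in the 8-day arm above 1.4 times the 4-day share widens it. That threshold assumes underlying total rates of 25% and 35%, and no particular shift in points should be attributed to this trial. The gap should be closed because the affected outcome sized the trial and the missed events are the kind of failure a shorter course might produce.

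**What to change.** Keep BAL-confirmed recurrence exactly as defined and add one chart-based outcome to Additional Outcomes. Suggested text:

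*Treated recurrent pneumonia: inclusion criterion 2b is met, with the radiograph scored from the final attending radiologist read already used for CPIS_clinical, and a new antibiotic course is started for pneumonia, 2 to 14 days after completion of initial therapy, whatever the airway or BAL status.*

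Add to Data Analysis: *BAL-confirmed recurrence or treated recurrent pneumonia will be reported by arm, by intention to treat, as a pre-specified sensitivity analysis against the same 10-point margin.* Reporting the two components separately, with airway status at the event, would show whether the loss differs between arms.

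The cost is chart abstraction and one analysis, with no additional BAL. A new field on the data collection tool may or may not be needed. The result should be labelled supportive because of lower specificity, possible dilution by false positives, and re-treatment decisions taken after blinding ends. It also cannot reach events after hospital discharge, when follow-up stops.
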